#### 1. Introduction

#### 1.1 Role of statistical analysis plan

This document is the statistical analysis plan of "Phase I/II investigator-initiated clinical trial of Human Papillomavirus (HPV)-targeting immunotherapeutic agent IGMKK16E7 on patients with high-grade cervical intraepithelial neoplasia (HSIL/CIN 2-3) (Trial Protocol No.: IGMKK/16E7/P1-2)". This plan was created before the registration of the first subject and finalized before data fixation. If changes or additions need to be made after Ver. 1 has been finalized, a revised version will be created after the change history and reasons are clarified.

#### 1.2 Changes from trial protocol

This analysis plan (Ver. 2) is a revision of Ver. 1 (May 27, 2019). In Ver. 2, the following revisions have been made in accordance with the revisions from V8.0 (dated January 10, 2020) to V13.0 (dated March 9, 2022) of the trial protocol.

- The analysis target of evaluating the improvement in cytology of HSIL/CIN 2-3 lesions, which is a secondary endpoint, was changed.
- Analysis methods for the following three secondary endpoints were added: 1) change in HPV 16 E7 molecule protein expression level (relative quantification value) and 2) disease control rate.

Furthermore, the HPV 16 E7 molecule protein expression level (absolute quantification value) before the start of administration and the HPV E7-specific immune response before the start of administration were added as stratification factors for the stratification analysis. Additionally, the following were added as exploratory analyses.

- 1) Investigation of the distribution of E7 protein expression level (absolute quantification value) before first administration.
- 2) Investigation of the relationship between the E7 protein expression level (absolute quantification value) before first administration and the improvement effect of the trial drug.
- 3) Investigation of the relationship between changes in the E7 protein expression level (relative quantification value) after administration and pathological judgment.
- 4) Investigation of the relationship between the presence or absence of HPV E7-specific immune response before first administration and the improvement effect of the trial drug.
- 5) Investigation of the relationship between the presence or absence of HPV E7-specific immune response after administration and pathological judgment.
- 6) Investigation of the relationship between the HPV E7-specific immune response SFC value after administration and pathological judgment.
- 7) Investigation of the relationship between the log-transformed HPV E7-specific immune response SFC value after administration and pathological judgment.

Moreover, we found that the analysis plan (Ver. 2) did not accurately reflect the changes in the

revision items of the clinical trial protocol; therefore, the following items were revised in this analysis plan (Ver. 2.1).

- When the protocol was revised to Ver. 2, the permitted range for subject visits was changed; however, this change was not reflected in the analysis plan. Therefore, the range of data adoption for the evaluation periods (Section 6.4.4) was changed to reflect the permitted range of visits in the protocol.
- When the protocol was revised to Ver. 5 of this protocol, we clarified the regulations regarding histology at week 24 for cases judged to be normal at week 16. Separately, we stipulated that follow-ups up to 24 weeks would be conducted according to the diagnosis by the attending physician at the facility 16 weeks after the first dose, except for cases judged to be CIN3 requiring treatment or invasive cancer. However, this content was not reflected in this analysis plan. Therefore, the above items were added to the primary endpoint (Section 4.1.1), and the handling of missing values (Section 6.5) was revised to reflect this content.

### 2. Purpose of trial

The aim of this clinical trial was to orally administer IGMKK16E7 (the trial drug) to patients with high-grade cervical intraepithelial neoplasia (HSIL/CIN 2-3) to confirm the safety of the trial drug and determine the clinical recommended dose.

#### 3. Trial method

#### 3.1 Trial design

The trial was a placebo-controlled randomized double-blind comparative study (Phase I/II clinical trial) of four dose parallel groups: placebo, low-dose (0.5 g/administration/day), intermediate-dose (1.0 g/administration/day), and high-dose (1.5 g/administration/day).

- Dosage and dose: The subject will take three sticks of trial drug once daily before breakfast. Consecutive administration for five days constitutes one course, with a total of four courses administered from the first administration (Day 1 to Day 5), Day 8 to Day 12, Day 22 to Day 26, and Day 50 to Day 54. However, the dose on Day 1 will be administered between meals in the hospital.
- Trial period: 16 weeks. Primary evaluation at 16 weeks after first dose.
- Follow-up period: eight weeks. Pathological evaluation (biopsy) was performed 16 weeks after the first dose to avoid missing patients who had progressed to invasive cancer; if the lesion was CIN3 or lower, the patients were again evaluated pathologically 24 weeks after the first dose. If a patient was diagnosed clinically as CIN3 or more at week 16, she received standard therapy.

### 3.2 Randomization

Registered subjects will be randomized in a 1:1:1:1 ratio for each of the four dose groups. The following three factors are used as allocation adjustment factors.

- 1. Diagnosis (HSIL/CIN2, HSIL/CIN3)
- 2. HPV genotype (HPV16 only, HPV16+other types)
- 3. Facilities (four facilities)

### 3.3 Target sample size

The sample includes 164 cases, with 41 cases each for the placebo group, low-dose group (0.5 g/administration/day), intermediate-dose group (1.0 g/administration/day), and high-dose group (1.5 g/administration/dose). Each group will have 10 cases with HSIL/CIN2 at the time of registration. See Section 5.2 of the trial protocol for the setting basis.

### 3.4 Interim analysis and data monitoring

No interim analysis is planned in this trial.

### 3.5 Trial schedule

Table 1 shows the trial schedule.

81.19	O b		]			0				•		•		0	•
ルポスコピー検査	O b		1							•			11	0	
建物量		O d, e	1			0	•			•		•	1	0	•
振振花(曲満hcg)		O d. *	0									•	10		•
VRE	(	o'	1												
V1627		00										•		0	
7 タンパク質発現 予定語刻語 湯細胞の		O g	0										0		
VE7特異的免疫炭后		0										•	1	0	
寬度終  ·他寬所見		•	•	•	•	•	•	•	•	•	•	•	1	0	٠
用基-併用意法 +															
住歴、会使住の確認	0	·				Į							1		
***		-												*	
・股用開始前に実施又は検子 営意取得後に、選択・除外書 同日に採取するE7タンパク	着幅黒を確認す 日準確認のため 着鬼現用の検4	る項目 ●: 銀用 の検査を実施す。 #を用いて検査を	開始後に実施 る 実施する。	する項目 △ : も: 向意取得新 d: 治験集の名	表面癌の疑い。 (90日以内のう (方前に開墾)	がある場合に美 データ(他院デー 「無い検査結果	(橋する項目) ローク、肥内データ (である(妊娠し)	・投与後10週で 不開)がある場 ている可能性が	通動調査の部 会、当該データ 無い)ことを確認	当康例と判断:   こて適格性を  辺する。 治験薬	わた症病のみ? 細形する。 読当す の役存(服用)に	実施する項目 ドるデータがない様 は、当該職業快速の	。 合われば同意取得 の実施日から10日	後に検査を実施す 131内に開始する。	φ.

## Table 1 Observation / survey and test items during the trial (follow-up) period

1

Item	Eligibi	ility nation period	Trial p	Trial period									Follow-up period		
	Initia 1 visit	Administrati on start day Day 1	(Wee k 1)	(Wee k 2)	(Wee k 3)	(Wee k 4)	(Wee k 5)	(Wee k 6–7)	(Wee k 8)	(Wee k 9)	(Wee k 10–15 )	(Wee k 16)	(Wee k 17–23 )	(Wee k 24)	At discontinuati on
Visit															
Permitted range of visit															
Prescription of trial drug															
Administratio n of trial drug															
Confirmation of drug administration status															
Consent acquisition															

Confirmation of selection / exclusion criteria								
Case registration								
HPV genotype test (for eligibility confirmation)								
HPV genotype test (central test)								
Histology (central pathological judgment)								
Histology (implementin g medical facility judgment)								
Histology								

Colposcopy								
Laboratory test								
Pregnancy reaction (serum hCG)								
HIV test								
HPV16E7 protein expression level								
E7 protein expression (cervical cells)								
HPVE7-specif ic immune response								
Subjective symptoms h / objective findings								

Concomitant drugs / therapies								
Confirmation of medical history and complications								
Confirmation of adverse events i								

 $\circ$ : Item that is implemented before the start of administration or confirms the test results;  $\bullet$ : Item that is implemented after the start of administration;  $\triangle$ : Item that is implemented in case of suspected invasive cancer;  $\bigcirc$ : Item that is implemented only on cases judged to be applicable in the follow-up survey at 16 weeks after administration

a: Implement test for selection/exclusion criteria confirmation after consent

b: Confirm eligibility based on applicable data in case there is data within 90 days prior to consent (data at another hospital, in-hospital data not required). Implement the test after consent in case there is no applicable data.

c: Implement test using E7 protein expression specimen collected on the same day

d: Confirm no problem with the test results (no possibility of pregnancy) before prescription of the trial drug. Administration of the trial drug shall start within 10 days from the day when the applicable laboratory test was conducted.

e: If the laboratory test was conducted on the date of consent and the administration start date was within 10 days from the date when the applicable test was conducted, there is no need to conduct a new test on the administration start date.

f: Perform at initial visit or on the administration start date. Confirm that the subject does not have HIV prior to prescribing the trial drug. Start administration of the trial drug within 14 days from the date when the applicable test was conducted.

g: Perform HPV genotyping on the same day using the collected specimen.

h: Subject shall record subjective symptoms in a health journal.

i: Confirm entries in the health journal during the administration period. The follow-up period (from week 17) shall only confirm adverse events that were clearly caused by the trial drug.

j: For subjects judged to be normal at week 16, perform only if a precancerous cervical disease was confirmed by colposcopy conducted on the same day (week 24).

k: In case retest is necessary because of the condition of the specimen, retest is permitted within 14 days from the date when the initial test was performed.

#### 4.1.2 Secondary endpoints

1) Regression rate at 24 weeks after the first dose

2) HPV E7-specific immune response: before trial drug administration, 16 and 24 weeks after the first dose.

The presence or absence of HPV E7-specific immune response at 16 weeks after the first dose and at 24 weeks after the first dose will be used as an endpoint. Separately, the presence or absence of HPV E7-specific immune response prior to the first dose will be used as a stratification factor for stratified analysis.

3) Change in HPV 16 E7 molecule protein expression level: at 16 and 24 weeks after the first dose.

HPV 16 E7 molecule protein expression level will involve measurements of the expression level (copy/ng) by relative quantification before first administration of the trial drug, and at 16 and 24 weeks after the first dose. The expression level by absolute quantification will also be measured only before the first administration of the trial drug. The magnitude and rate of change of the expression level (relative quantification value) from before first administration to 16 and 24 weeks after the first dose will be the endpoint. Separately, the expression level (absolute quantitative value) before the first dose is used as a stratification factor for stratification analysis. For this stratification factor, two categories of "below median" and "above median" and three categories of "below first tertile," "above first tertile, below second tertile," and "above second tertile" will be used.

4) Improvement in cytology\* of HSIL/CIN 2-3 lesions: at 16 and at 24 weeks after the first dose. Changes in lesions in cytology are judged by any of the following in subjects diagnosed with HSIL at the time of registration.

PR: Change to LSIL, ASC-US, or NILM

SD: No change from HSIL

PD: Change to SCC

NE: Change to AGC or ASC-H

\* Cytology: Cytological tests of the cervix will be conducted before trial drug administration, nine weeks after the first dose, 16 and 24 weeks after the first dose.

5) Percentages of "CR," "PR," "SD," and "PD" in the pathological improvement indicators of cervical intraepithelial neoplasia lesions: at 16 and 24 weeks after the first dose.

6) Presence or absence of changes in the HPV16: at 16 and 24 weeks after the first dose.HPV genotype test: conducted before trial drug administration, 16 and 24 weeks after the first dose (applicable cases only) to measure the HPV genotype.

7) The one with better results at both 16 weeks and 24 weeks after the first dose is considered the best response determination.

8) Disease control rate: percentage of subjects with histology of CIN3 at registration improving to CIN2 or lower at 16 and 24 weeks after the first dose.

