### 6. Statistical analysis policy

### 6.1 Significance level and confidence level

Unless otherwise specified, tests are two-sided tests with a significance level of 0.05, and the confidence interval is a two-sided confidence interval with a confidence coefficient of 95%.

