### 6.2 Multiplicity adjustment

Given that this trial is a phase I/II trial, multiplicity was not considered in either pairwise comparisons or dose-response evaluations using the maximum contrast method of the response rate, which is the primary efficacy endpoint, between each dose group and the placebo group. Additionally, multiplicity of tests will not be considered when tests are repeated for secondary endpoints.

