### 7.3.2. Analysis of secondary endpoints

Target FAS, PPS

population:

Analysis 1) Regression rate at 24 weeks after the first dose

content: The same analysis as the primary and secondary analyses of the primary endpoint is conducted.

2) HPV E7-specific immune response is calculated for FAS and PPS for each group at 16 and 24 weeks after the first dose:

The 95% confidence interval is also calculated using the Clopper–Pearson method. Furthermore, the same analysis is conducted by stratification according to the stratification factors for FAS.

3) Change in HPV16 E7 molecule protein expression level (relative quantification value)

For FAS and PPS, summary statistics are calculated by group for the HPV16 E7 molecule protein expression level before the first administration, at 16 and 24

weeks after the first dose, as well as for the magnitude and rate of change at 16 and 24 weeks after the first dose. Furthermore, comparisons of the magnitude and rate of change between each dose group and the placebo group are conducted using the Wilcoxon rank sum test. The same analysis is conducted for FAS by stratification using the stratification factors. Additionally, for FAS and PPS, a spaghetti plot of HPV16 E7 molecule protein level is created for each group, from the first administration of the trial drug in each subject to weeks 16 and 24.

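### The change in E7 expression is tested between groups without using the patient's own pre-dose relative value as a covariate: a valid but inefficient analysis, on two scales that can disagree

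*SAP*

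**What the plan says.** Section 4.1.2, item 3, makes the endpoint "The magnitude and rate of change of the expression level (relative quantification value) from before first administration to 16 and 24 weeks". The relative value is to be measured before dosing and again at weeks 16 and 24.

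Section 7.3.2, item 3, gives the test: "comparisons of the magnitude and rate of change between each dose group and the placebo group are conducted using the Wilcoxon rank sum test". No covariate is named.

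The pre-dose level has one other role: "the expression level (absolute quantitative value) before the first dose is used as a stratification factor for stratification analysis", in median or tertile categories. Section 7.3.2 then adds: "The same analysis is conducted for FAS by stratification using the stratification factors". No pooled, stratum-adjusted test is described.

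Section 6.1 sets the level: "tests are two-sided tests with a significance level of 0.05". Section 6.2 states that "multiplicity of tests will not be considered when tests are repeated for secondary endpoints". The SAP gives no variability, pre-post correlation, effect size or power for this endpoint and makes no power claim for it.

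**The concern.** Expression quantities often vary multiplicatively and are skewed to the right. That is an assumption here, because the SAP shows no data. If it holds, the planned measures have different weaknesses.

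- **Magnitude of change** (post minus pre) mixes the treatment effect with the starting level. A fall from 10,000 to 5,000 counts for more than a complete loss from 100 to 0.
- **Rate of change** removes that scale problem but carries the full noise of the single pre-dose measurement.

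A model with the pre-dose value as covariate avoids both. At stake is a needlessly insensitive comparison of E7 expression with placebo. There are also two co-reported tests that can point different ways for reasons of scale, and the SAP does not say which is to be read. With 3 doses × 2 measures × 2 time points there are 12 such tests per analysis set.

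**Working it through.** **Inputs from the SAP.** Section 3.3: "The sample includes 164 cases, with 41 cases each for the placebo group", and the same for each dose group (4 × 41 = 164, which agrees). Section 3.2: "Registered subjects will be randomized in a 1:1:1:1 ratio for each of the four dose groups". Two-sided alpha is 0.05. The SAP gives no power figure for this endpoint, so there is none to reproduce.

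**Assumed inputs.** Log-normal pre- and post-dose values; SD 0.5 to 2.0 in natural-log units; pre-post correlation ρ from 0.2 to 0.9; the drug multiplies the post-dose value; rate of change = (post − pre)/pre; all 41 per arm observed. The placebo median is stable, halved, or down to one fifth.

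**Effect size.** It is set so that ANCOVA of log post-dose on log pre-dose has about 80% power:

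δ = (1.960 + 0.842) × SD × √(1 − ρ²) × √(2/41) = 0.619 × SD × √(1 − ρ²)

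For SD 1 and ρ 0.5, δ = 0.619 × 0.866 = 0.536, a ratio to placebo of exp(−0.536) = 0.585.

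**Check by formula for the rate of change.** It ranks patients as the log ratio does. The log ratio has variance 2·SD²(1 − ρ), and the ANCOVA residual has SD²(1 − ρ²), so the relative efficiency is (1 + ρ)/2. The Wilcoxon test on normal data adds a factor 3/π = 0.955. Power is then about Φ(2.802 × √(0.955(1 + ρ)/2) − 1.960):

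- ρ = 0.2: √0.573 = 0.757; Φ(0.161) = 56%
- ρ = 0.5: √0.716 = 0.846; Φ(0.411) = 66%
- ρ = 0.9: √0.907 = 0.952; Φ(0.709) = 76%

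This agrees with the simulated range of 55% to 76%.

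**Simulated power** (3,000 runs per setting with stable placebo, 700 with placebo drift). Log ANCOVA has 77–80% and rank ANCOVA 70–78%.

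| Placebo median | Raw-change power | Raw-change loss (points) | Rate-of-change loss (points) |
|---|---|---|---|
| Stable | 36–67% | 11–42 | 3–24 |
| Halved | 16–30% | 49–63 | 3–22 |
| One fifth | 4–15% | 62–74 | 3–19 |

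Losses are against log ANCOVA. With a stable placebo, the smallest raw-change loss is at SD 0.5, ρ 0.9 and the largest at SD 2.0, ρ 0.2. In between, at SD 1 and ρ 0.5, power is 77% (log ANCOVA), 50% (raw) and 64% (rate). Type I error is about 5% for every test.

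**Second setting: fixed 4-fold fall, SD 1 log10, stable placebo** (2,000 runs).

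| ρ | Raw change | Rate of change | Rank ANCOVA | Log ANCOVA |
|---|---|---|---|---|
| 0.3 | 38% | 62% | 78% | 81% |
| 0.5 | 44% | 74% | 84% | 87% |
| 0.7 | 67% | 92% | 93% | 96% |

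Here the raw-change and rate-of-change tests gave opposite significance verdicts in 26–31% of trials, and in 35–51% if placebo expression also halves.

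**Does raw change rank by starting level?** The Spearman correlation of raw change with the pre-dose value in the placebo arm is −0.18 to −0.59 when its median is stable, −0.58 to −0.89 when it halves, and −0.80 to −0.99 at one fifth. In the treated arm of the 4-fold setting it is −0.72 to −0.74.

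**Do the stratified repeats help?** They use the absolute value, whereas the endpoint is built on the relative value. They leave about 41/2 ≈ 20 (median) or 41/3 ≈ 14 (tertiles) per arm per stratum, and no pooled test puts the strata together again.

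**The case against.** The strongest reply is that nothing here is wrong. An unadjusted Wilcoxon test on change is valid and prespecified. The SAP claims no power for this endpoint, and section 4.1.1 ties the recommended dose to the regression rates. Reporting both scales also answers the worked example: 10,000 to 5,000 is −50% and 100 to 0 is −100%, so the rate of change ranks the complete loss first. All of this stands.

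The size of the loss also depends wholly on the inputs. An SD of 1 log10 means a 95% range of 10^(2 × 1.96) = 10^3.92, roughly 8,300-fold. With the same 4-fold fall at SD 0.5 log10, raw change has about 85%, 93% and 98% power at ρ 0.3, 0.5 and 0.7, while the rate of change and the adjusted rank analysis both have at least 99.6%. At SD 0.3 log10 all three have at least 99.8%. Smaller effects reopen the gap. This is why only a range can be given.

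A reader might infer three stronger points that the SAP does not support:

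- *Some 40 points of power are lost.* That is the top of the stable-placebo range, for raw change only, at large SD and low correlation. The rate-of-change test, also planned, loses far less.
- *Raw change mostly ranks patients by how high they started.* This holds only where expression falls substantially. The SAP does not say that it falls on placebo.
- *A working dose will look inactive in the lesion.* No decision rests on this test, and Table 1 lists the E7 protein specimen as cervical cells.

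The reply does not explain why the pre-dose relative value, already in hand, should stay out of the comparison.

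**Conclusion.** The point holds as one of efficiency and interpretation. Both planned between-group tests leave out the pre-dose relative value as a covariate, and the stratified repeats do not recover what this costs. Against log ANCOVA at about 80% power, with log-normal data, 41 per arm and a stable placebo median, the cost is about 11 to 42 points for raw change and 3 to 24 for rate of change. The raw-change loss is larger if expression falls in all arms. These figures rest on assumed SDs, correlations and effects. At week 24, where only follow-up cases are measured, fewer than 41 per arm may contribute.

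No inflated error rate or bias should be read into this. The endpoint is an unpowered secondary one in a phase I/II trial, so the change is desirable but not essential.

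**What to change.** In section 7.3.2, item 3, name one baseline-adjusted between-group analysis at each of weeks 16 and 24: ANCOVA of the log post-dose relative value on the log pre-dose relative value, each dose against placebo, reported as a fold ratio to placebo with its 95% confidence interval.

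State a rule for zeros or non-detects. The SAP has one only for the SFC value (section 7.3.3, item 7), and the rate of change is itself undefined when the pre-dose value is zero.

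Name rank ANCOVA as the alternative if zeros are common. It is a different method that gives no fold ratio. It can also be slightly less powerful than the rate-of-change test when the pre-post correlation is about 0.9: in one such setting (SD 2, log ANCOVA at 90%) it had 83% against 86%.

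Keep magnitude and rate of change as descriptive summaries, and align section 4.1.2, item 3, with this.

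The cost is SAP wording, one standard model and a zero rule. No new data are needed.

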### 4.1.3 Exploratory endpoints

1) Investigate distribution of the E7 protein expression level (absolute quantification value) before first administration.

2) Investigate the relationship between the E7 protein expression level (absolute quantification value) before first administration and the improvement effect of the trial drug.

3) Investigate the relationship between changes in the E7 protein expression level (relative quantification value) after administration and pathological judgment.

4) Investigate the relationship between the presence or absence of HPV E7-specific immune response before first administration and the improvement effect of the trial drug.

5) Investigate the relationship between the presence or absence of an HPV E7-specific immune response after administration and pathological judgment.

6) Investigation of the relationship between the HPV E7-specific immune response SFC value after administration and histopathological regression. [For the HPV E7-specific immune response, data on continuous values of the E7-specific immune response (SFC/10^6 cells) are obtained. Hence this item will be referred to as the HPV E7-specific immune response SFC value].

7) Investigate the relationship between the log-transformed HPV E7-specific immune response SFC value after administration and histopathological regression.

